1.1 To study the effect of an environmental label on the environmental impact of ingredients and ready- to-eat dish choice in a virtual supermarket.	Mean of PEF  score for 100g of each ingredient selected and PEF score for 100g of the ready-to-eat dish in the "everyday scenario".	
 
An environmental label will lower the environmental impact of the food choices made by the participants compared to no label.
 
The effect of the environmental label will be greater when choosing a ready-to-eat dish compared to when choosing ingredients.
 
				
1.2 To investigate whether the environmental label is informative and likely to help individuals to choose environmentally friendly food options when they	Mean PEF score for 100g of each ingredient selected and PEF score for 100g of the ready-to-eat dish in the "everyday scenario" and the "environmentally-friendly scenario".	
 
The reduction of the environmental impact of the foods chosen in the "environmentally-friendly scenario" compared to the "everyday scenario" will be greater for participants in the
 
				

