## **OBJECTIVES, OUTCOMES MEASURES AND HYPOTHESES**

<sup>1 PEF score is the "Product Environmental Footprint". Details regarding its calculation is described in the paragraph "Creation of an environmental score" (page 9).

are encouraged to make environmentally friendly food choices.		environmental label condition than in the no label condition.
2.1 To study the effect of an environmental label on the nutritional quality, liking, familiarity, level of process and price of ingredients and ready-to- eat dish choices in a virtual supermarket.	Secondary objectives The following variables will be calculated for the 3 ingredients (average) and for the ready-to-eat dish chosen in the "everyday scenario": FSA scores Liking Familiarity NOVA score (only for the average of the 3 ingredients) Price per calorie (continuous variables)	
 
The environmental label will have an impact on the nutritional quality (FSA score), liking, familiarity, NOVA score and price of the foods chosen by the participants.
 

2.2 To investigate the relationships between food motives and the effect of an environmental label on ingredients and ready-to- eat dish selection in a virtual supermarket.	
 
Mean PEF score for 100g of each ingredient selected and PEF score for 100g of the ready-to-eat dish in the "everyday scenario".
 
Level of ethical concern (questionnaire score)
 
	
 
The environmental label will be more effective in reducing the environmental impact of food choices in participants with higher levels of ethical concern when making food choices.
 

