## STATISTICAL ANALYSES

All statistical analyses will be performed using SAS version 9.4. The level of significance will be set at p < 0.05 for all pre-registered analyses.

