### Overview of the statistical analysis

impact of ingredients and ready-to- eat dish choice in a virtual supermarket.		- Type of food (I  / RTEd  )		If label*type_of_food interaction is not significant, it will be removed from the model.
1.2. To investigate whether the environmental label is informative and likely to help individuals to choose environmental- friendly food options when they are encouraged to make environmental- friendly food choices.	Mean of PEF score for 100g of each ingredient selected and PEF score for 100g of the ready- to-eat dish.	- Environmental label (0= no / 1= yes) - Scenario ("everyday scenario"/ "environmental- friendly scenario") - Type of food (I / RTEd)	Data from the two labelling conditions and the two scenarios	Mixed model analysis with random effect of participants. Mixed model analysis with random effect of participants. PEF = label (0/1) + type_of_food ( I/RTEd ) + scenario (everyday/environmental) + label*type_of_food + label*scenario + scenario*type_of_food Non-significant interactions will be removed from the model. If the labelling*type_of_food or the scenario*type_of_food interaction is statistically significant: • For the 3 ingredients chosen (Task 1) PEF = labelling + scenario + labelling * scenario • For the ready-ot-eat dish chosen (Task 2) PEF = labelling + scenario + labelling * scenario

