#### MODEL 1.2:

- Mixed model analysis will be used to test the effect of *labelling* (categorical variable: yes or no), *type\_of\_food* (categorical variable: ingredients or ready-to-eat dish), *scenario* (categorical variable: "everyday scenario" or "environmentally friendly scenario"),*labelling\*scenario*, *labelling\*type\_of\_food* and *scenario\*type\_of\_food* interactions on PEF scores, with random effect of participants to account for correlation between repeated measures. Non-significant interactions will be removed from the model.
- If the *labelling\*type\_of\_food* or the *scenario\*type\_of\_food* interaction is **statistically** significant, two mixed model analysis will be carried out for the home-cooked dish (average of the 3 ingredients) and for the ready-to-eat dish separately. These models will test the effect of *labelling* (categorical variable: yes or no), *scenario* (categorical variable: "everyday scenario" or "environmentally friendly scenario") and *labelling\*scenario* interaction on PEF scores, with random effect of participants to account for correlation between repeated measures.

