### Sample size

We powered primary analyses in order to detect a d=0.50 effect size of labelling on PEF scores based the results of a previous randomised control trial that tested the effect of an environmental label on food choices (Camilleri, 2019). A sample size of 122 participants will be required for 80% power at  $\alpha$  = 0.05 (SAS 9.4). We will recruit a sample of 130 participants to account for potential data loss due to technical problems.

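### Primary objective 1.2 has no fixed test: Model 1.2 can drop the label-by-scenario term, and it splits by task on other interactions without saying which result counts

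*Combined protocol and SAP*

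**What the plan says.** The objectives table states hypothesis 1.2 once, for the chosen foods as a whole: "The reduction of the environmental impact of the foods chosen in the" environmentally-friendly scenario, against the everyday one, will be larger in the "environmental label condition than in the no label condition". In model terms this is the label-by-scenario interaction on PEF score.

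Under Primary analyses, Model 1.2 contains label, type of food (ingredients or ready-to-eat dish), scenario and the three two-way interactions, "with random effect of participants to account for correlation between repeated measures". Two rules follow, both also in the overview table:

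- "Non-significant interactions will be removed from the model". No interaction is exempted.
- "If the labelling*type_of_food or the scenario*type_of_food interaction is statistically significant", then "two mixed model analysis will be carried out for the home-cooked dish (average of the 3 ingredients) and for the ready-to-eat dish separately". Each task model contains label, scenario and their interaction, and no removal rule is given for it.

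The opening of Statistical analyses adds: "The level of significance will be set at p < 0.05 for all pre-registered analyses". The plan has no multiplicity rule. The Sample size section reads: "We powered primary analyses in order to detect a d=0.50 effect size of labelling on PEF scores". It gives no effect size for label-by-scenario.

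**The concern.** Three things are left open for a primary objective.

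1. **Removal.** In the pooled branch, a non-significant label-by-scenario term leaves the model. It has been tested by then, but the final model carries no estimate or confidence interval for it, and the plan does not commit to reporting the earlier fit. Since the sample size was set for labelling alone, that interval is needed to interpret a non-significant result.
2. **Trigger.** Label-by-type and scenario-by-type do not show whether the label-by-scenario effect differs between tasks. The three-way term that would show it is never fitted.
3. **Decision.** After a split there can be three label-by-scenario tests, each at 0.05, and no rule says which one answers the objective. Both the number of tests and the meaning of success then depend on other interactions in the data.

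Keeping the pooled term would not be enough by itself. If the participant effect is a random intercept only, the pooled test treats a participant's scenario changes in the two tasks as independent.

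Model 1.1 has a related gap: it removes label-by-type when not significant, although a larger label effect for ready-to-eat dishes is its own second hypothesis.

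**Working it through.** **Inputs from the plan.** 122 participants, 1:1, so 61 per arm; alpha 0.05, taken as two-sided; four PEF values per participant (two tasks, two scenarios).

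**Assumed, because the documents give no SD or correlation.** Total variance 1; participant-intercept share 0.1 or 0.5; rho, the correlation between a participant's scenario changes in the two tasks, 0 to 0.5; participant-by-type variance either zero or equal to the participant-by-scenario variance; scenario-by-type effect 0, 0.2 or 0.4 SD. Ranges below cover these settings. Each case has 40,000 simulated trials with no true label-by-scenario effect.

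**Step 1. The plan's own figure.** For d = 0.50, 80% power and two-sided 0.05, the normal formula gives 126 and the t-test 128, against 122 in the plan. At 61 per arm power is 78.9% or 78.2%. The gap is small and does not bear on this point, so 61 per arm is used.

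**Step 2. Whole procedure at rho 0.** The pooled test decides if there is no split. False-positive rate by reading:

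| Scenario-by-type effect | Split occurs | Either task counts | Pooled or either task | Both tasks needed |
|---|---|---|---|---|
| 0 | about 10% | 5.5% | 5.7% | 4.5–4.6% |
| 0.2 SD | 25–38% | 6.0–6.7% | 6.4–7.4% | 3.1–3.6% |
| 0.4 SD | 66–88% | 8.1–9.0% | 9.2–10.8% | 0.8–1.9% |

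For reference, two independent tests at 0.05 give 1 − 0.95² = 9.75%.

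**Step 3. The same at rho 0.5.**

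| Scenario-by-type effect | Either task counts | Pooled or either task | Both tasks needed |
|---|---|---|---|
| 0 | 8.4–14.5% | 8.6–14.7% | 7.7–14.3% |
| 0.2 SD | 8.7–13.3% | 9.3–15.1% | 5.2–11.7% |
| 0.4 SD | 8.9–10.3% | 11.0–16.2% | 1.0–3.9% |

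Each task test taken alone holds 4.7–5.3%.

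**Step 4. Power if both tasks are needed.** Suppose the task-averaged test has 80% power (noncentrality 2.80). With rho 0 and equal standard errors, each task has noncentrality 2.80/√2 = 1.98, about 51% power, so both succeed in about 0.51² = 26%. Over rho 0 to 0.5 and task standard-error ratios of 1 to 2 (same raw effect in both tasks), the range is 26–53%.

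**Step 5. The pooled random-intercept test.** Let a = rho/(1 − rho), and let b be participant-by-type variance over residual variance. The pooled residual has 120 + 120 + 121 = 361 df, and

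true variance / assumed variance = (1 + 2a) / {[120(1 + 2a) + 120(1 + 2b) + 121]/361}.

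- rho 0.3 (a = 0.429): 1.445 with b = 0 and 1.183 with b = a, giving error rates of 10.3% and 7.2%.
- rho 0.5 (a = 1): 3 × 361/601 = 1.802 and 3 × 361/841 = 1.288, giving 14.4% and 8.4%.

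Simulation agrees: 4.8–5.2% at rho 0, 5.7–6.7% at 0.1, 6.9–10.4% at 0.3 and 8.3–14.6% at 0.5. A test on each participant's task-averaged change (120 df) holds 4.7–5.1% throughout. In one simulated data set the random-intercept standard error was 0.103. The task-averaged change gave 0.143, as did a mixed model with participant-by-scenario and participant-by-type effects.

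**Step 6. Precision of a single test.** The 95% half-width is t(0.975; 120) × √(2/61) = 1.980 × 0.181 = 0.36 SD of the task-averaged change; 80% power needs 0.51 SD. For label-by-type in Model 1.1 the half-width is likewise 0.36 SD of a participant's between-task difference.

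**The case against.** The strongest reply has four parts.

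- **Removal is a reporting matter.** The interaction is tested before it is dropped, the task models keep it, and nothing says that only the final model will be reported. This is fair. What is missing is a commitment to give the estimate and interval. The plan can make such an exception: Model 2.2 names only label-by-type for removal and leaves its hypothesised term, label-by-ethical-score, in place.
- **The task models naturally replace the pooled one**, so three tests is the least natural reading. That may well be the intention, but it still does not say whether one task or both must succeed. At rho 0 and 0.4 SD, those two readings give 8.1–9.0% and 0.8–1.9%.
- **The error rates rest on unknowns.** This is true. At rho 0 there is no inflation if both tasks are needed, and little under any reading if no trigger interaction exists. The random-intercept point depends on reading the participant effect as an intercept and on rho being positive; at 0.1 it is minor, and negative values, where the test would be conservative, were not examined.
- **Separate task answers fit the objectives.** The objectives table lists two measures, and the background expects the tasks to differ. This stands: averaging over tasks is a choice. It supports task results planned in advance, but not a split triggered by other interactions.

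None of this supplies the missing decision rule, which is a gap in the text and needs no assumption to establish.

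**Conclusion.** The concern holds and should be fixed before analysis. Three facts follow from the text alone: the hypothesised term is not exempt from removal, the split triggers do not test it or its variation by task, and no rule says which result answers objective 1.2. The numerical consequences are illustrative. At rho 0 with a 0.4 SD scenario-by-type effect, the unstated reading moves the false-positive rate between about 1% and 11%. Requiring both tasks cuts power to 26–53% where a task-averaged test would have 80%. The random-intercept issue is conditional on positive rho. Because rho is undocumented and the remedy is cheap, it is better to choose a test that holds its level in either case. The data themselves are not compromised.

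**What to change.** In Model 1.2:

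- Always keep label-by-scenario. Report its estimate and 95% CI, averaged over the two tasks, as the single test of objective 1.2, whatever the other interactions show.
- Base it on each participant's task-averaged change between scenarios, compared by arm, or on a mixed model with participant-by-scenario and participant-by-type random effects. Do not use a pooled model with a random intercept only.
- Report the label-by-scenario contrast for each task with a 95% CI as supportive, not conditional on any interaction p-value.

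Averaging should be a deliberate decision, because the scales differ: the top limits in Table 5 are 6.09 mPt/kg for ingredients and 3.23 for ready-to-eat dishes. If one answer per task is preferred, state that now and use two ungated task tests with Holm correction (simulated false-positive rate 4.9% at rho 0 and 4.6% at rho 0.5).

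In Model 1.1, keep label-by-type and report its estimate and CI whatever its p-value.

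The cost is SAP wording, one change score per participant or two extra random effects, and slightly more reporting; no new data. At rho 0 the interval is under 1% wider than the random-intercept one. At rho 0.1 to 0.5 the standard error is about 3% to 34% larger (square roots of 1.065, from the step 5 formula at rho 0.1 with b = a, and of 1.802), but there the random-intercept interval is too narrow.

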### Secondary analyses

For the first secondary analysis (MODEL 2.1), mixed model analysis will be used to test the effect of *labelling* (categorical variable: yes or no), *type\_of\_food* (categorical variable: ingredients or ready-to-eat dish) and *labelling\*type\_of\_food* interaction on 4 dependent variables, with random effect of participants to account for correlation between repeated measures. We will only look at the data from the first scenario ("everyday scenario"). The 5 mixed model analysis that will be carried out are:

- FSA = labelling (categorical variable: yes or no), type\_of\_food (categorical variable: ingredients or ready-to-eat dish) and labelling\* type\_of\_food interaction
- Liking = labelling (categorical variable: yes or no), type\_of\_food (categorical variable: ingredients or ready-to-eat dish) and labelling \* type\_of\_food interaction
- Familiarity = labelling (categorical variable: yes or no), type\_of\_food (categorical variable: ingredients or ready-to-eat dish) and labelling\* type\_of\_food interaction
- Price per calories (€/kcal) = labelling (categorical variable: yes or no), type\_of\_food (categorical variable: ingredients or ready-to-eat dish) and labelling\* type\_of\_food interaction

If the *labelling\*type\_of\_food interaction* is not significant, it will be removed from the models.

ANOVA model will be used to test the effect of *labelling* (categorical variable: yes or no) on NOVA score for task 1 (for the 3 ingredients chosen). We will only look at the data from the first scenario ("everyday scenario").

- For the second secondary analysis (**MODEL 2.2**), we will only use "everyday scenario" data.
  - Mixed model analysis will be used to test the effect of *labelling* (categorical variable: yes or no), *type\_of\_food* (categorical variable: ingredients or ready-to-eat dish), *labelling\*type\_of\_food* interaction, *Ethic\_score* (continuous variable) and *labelling\* Ethic\_score* interaction on PEF scores, with random effect of participants to account for correlation between repeated measures. If the *labelling\*type\_of\_food* interaction is not significant, it will be removed from the model.
  - If the interaction between the labelling condition and the type of food is statistically significant., two ANCOVA models will be carried out for the home-cooked dish (average of the 3 ingredients) and for the ready-to-eat dish separately. ANCOVA models will be used to test the effect of *labelling* (categorical variable: yes or no), *Ethic\_score* (continuous variable) and *labelling\*Ethic\_score* interaction on the mean PEF score.

### Sensitivity analyses

- Sensitivity analysis will be carried out to analyse if the results found for MODEL 1.1. remain the same when aim guessers are excluded.
- **MODEL 1.1.** will be adjusted for age, sex, level of education and BMI.
- **MODEL 1.1.** (raw and adjusted) will be replicated for the GHGe from the Agribalyse database instead of the PEF score.

### Exploratory analyses

Descriptive analyses of the answers to the investigation questionnaire will be performed.

1/ We will calculate the scores of participants responding to the following questions depending on the label condition and the scenarios ("everyday" / "environmentally friendly"):

• How much did taste / nutritional quality / environmental impact / packaging size / presumed price influence participant's food choice in the virtual supermarket? (5 possible answers ranging from "strongly disagree" to "strongly agree")

2/ We will calculate the scores of participants responding to the following questions depending on the label condition:

- What participants understood when asked to make food choices that are "good for the planet" (8 possible answers).
- Participant's perception of their capacity to distinguish 2 foods depending on their environmental impact (5 possible answers ranging from "strongly disagree" to "strongly agree").

3/ We will calculate the scores of participants, in the labelling condition, responding to the following questions:

- If they noticed the label (0=they did not notice the presence of the label on the products chosen or thought that the label was present on less than half of the products chosen /1=the participant thought the label was present on all of the products chosen or on more than half of them).
- If they understood the environmental label presented on the foods in the virtual supermarket (0=the participant did not answer correctly / 1=the participant answered correctly).
- If they used the environmental label when making food choices (we will categorize the scale ranging from 0 to 100 into 4 parts).

Further exploratory analyses will be conducted to have a broader understanding of the effects of the environmental label on food choices and are summarised in **Table 6**.

Data used of the analysis	Dependent variable	Independent variables	Statistical analysis
Both labelling conditions and the 2 scenarios will be considered	Importance of food choice motives for each scenario (taste, nutritional quality, environmental impact, presumed price and packaging size) Continuous variables	
 
Environmental label (0= no / 1= yes)
 
Scenario ("everyday scenario"/ "environmental-friendly scenario")
 
	
Data for participants in the "label condition" only	Mean PEF scores	
 
Attention paid by the participant to the label (0=they did not notice the presence of the label on the products chosen or thought that the label was present on less than half of the products chosen /1=the participant thought the label was present on all of the products chosen or on more than half of them)
 
Type of food (I / RTEd)
 
Scenario ("everyday scenario")
 
Use of the label by the participant (continuous variable ranging from 0 to 100)
 
Type of food (I / RTEd)
 
Scenario ("everyday scenario")
 
	Mixed model analysis

	
 
Time spent to carry out each shopping task (continuous variable)
 
Environmental label (0= no / 1= yes)
 
Type of food (I / RTEd)
 
	
	
 
Score obtained for the question regarding the knowledge about the environmental impact of food systems (continuous variable).
 
Environmental label (0= no / 1= yes)
 
Type of food (I / RTEd)
 
	
	(knowledge_score*labelling interaction will be interesting to analyse in order to test the moderating effect of knowledge on the environmental impact of food choices)	
Mean FSA scores	
 
The average ratings for items in the health subscale of the FCQ
 
Environmental label (0= no / 1= yes)
 
Type of food (I / RTEd)
 
	

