- 3) From this will follow a food choice motivation guestionnaire. We will use the adaptation of the Food Choice Questionnaire (Steptoe et al., 1995) for the French population (Cottet et al., 2017). This version includes 24 items that are grouped in 9 subscales (health, convenience, sensory appeal, natural content, ethical concerns, weight control, mood, familiarity and price). In order to have a better understanding of the sustainability motives consumers have for selecting their food, we will also ask independently the "Environmental welfare" subscale from the recently published Sustainable Food Choice Questionnaire (SUS-FCQ) (Verain et al., 2021). This subscale is composed of 5 items and its reliability was considered, by its authors, high enough to be used independently. The 5 items were translated in French and back-translated to English. For each item, participants will be asked to give a score ranging from 1 to 4 (1= not at all important, 2= a little important, 3= moderately important and 4 = very important). We will calculate the average scores for the "ethical" subscale of the FCQ and for the "environmental welfare" subscale of the SUS-FCQ. We will use the score with the highest Cronbach's coefficient in the analyses. The Food Choice Questionnaire will be complemented with questions regarding potential changes in food consumption habits that will inform future research work and will not be analysed as part of the present study. This latter was studied by (Gadema & Oglethorpe, 2011). Will follow, questions evaluating participants' declared capacity to make food choices based on the environmental impact or the nutritional quality of products.

<sup>3 These questions have the purpose to inform an additional research project.

4) A socio-demographic questionnaire to collect data regarding the participants (age, gender, level of qualification, etc.) will be completed by the participants.

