2.2. To investigate the relationships between food motives and the effect of an environmental label on ingredients and ready-to- eat dish selection in a virtual supermarket.	Mean of PEF scores for 100g of each ingredient selected and PEF score for 100g of the ready- to-eat dish.	
 
Environmental label (0= no / 1= yes)
 
The average ratings for items in the ethical subscale of the FCQ (Ethic_score)
 
Type of food (I / RTEd)
 
	Data from scenario 1 only (everyday scenario)	Mixed model analysis with random effect of participants. - PEF = labelling + Ethic_score + type_of_food + labelling* type_of_food + labelling* Ethic_score If label*type of food interaction is statistically significant: 2 ANCOVA models • For the 3 ingredients chosen (Task 1) - PEF = labelling + Ethic_score + labelling* Ethic_score • For the ready-ot-eat dish chosen (Task 2) - PEF = labelling + Ethic_score + labelling* Ethic_score

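### Two exploratory label-arm models in Table 6 relate self-reported attention to and use of the label to PEF without any participant covariate, so they can show an apparent effect of use even if the label does nothing

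*Combined protocol and SAP*

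**What the plan says.** The Exploratory analyses section introduces Table 6 this way: "Further exploratory analyses will be conducted to have a broader understanding of the effects of the environmental label on food choices". One block of the table is restricted to the label arm and has mean PEF as outcome. It contains two mixed models. The first predictor is "Attention paid by the participant to the label", a 0/1 variable based on how widely the participant thought the label was present on the chosen products. The second is "Use of the label by the participant (continuous variable ranging from 0 to 100". Each has its own list of other terms: type of food, and scenario with only the everyday level named. The table is broken in the extracted text, but both lists are readable and neither contains a participant characteristic.

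A measure of concern is collected. Under Questionnaires after the shopping experience, the ethical subscale of the FCQ and the environmental welfare subscale of the SUS-FCQ are both averaged, and the one with the higher Cronbach's alpha becomes Ethic_score. It enters only Model 2.2 ("PEF = labelling + Ethic_score + type_of_food" plus interactions with labelling). The one planned covariate adjustment, under Sensitivity analyses, concerns Model 1.1 and uses age, sex, education and BMI.

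**The concern.** Attention and use are not assigned. They are chosen by participants who all received the label and its pop-up explanation, and they are reported after shopping. A person who cares about the environment may both use the label more and pick lower-PEF food whether or not a label is present. The use coefficient then picks up that person's prior preference. The section gives no caveat that these predictors are non-randomised, and it offers the table as a way to understand the label's effects. A negative coefficient for use would invite the reading that the label works when people use it. At stake is the interpretation of two exploratory coefficients.

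**Working it through.** **Inputs.** The plan gives no figure for these two models, so there is nothing of its own to reproduce. Under Sample size, 130 participants are to be recruited, and allocation is 1:1, so the label arm has 130/2 = 65. Alpha is 0.05, taken as two-sided because the plan does not say. The correlations are assumptions: *a* between concern and label use, and -*b* between concern and a participant's mean PEF over the two everyday dishes. The reliability of Ethic_score is assumed to be 0.8. The label is set to have no effect.

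**Step 1: the spurious correlation.** If concern is the only link between use and PEF, their correlation is r = -ab. If a = 0 or b = 0, r = 0 and the test keeps its 5% level.

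**Step 2: how often it is significant.** By Fisher's transformation, δ = atanh(ab) × √(65 - 3), and the rejection rate is P(Z > 1.96 - δ) + P(Z < -1.96 - δ). At (0.5, -0.5), ab = 0.25 and δ = 0.255 × 7.87 = 2.01, so the rate is P(Z > -0.05), about 52%.

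**Step 3: after adding Ethic_score.** With reliability 0.8 the partial correlation is -0.2ab / √[(1 - 0.8a²)(1 - 0.8b²)]. At (0.5, -0.5) this is -0.05/0.80 = -0.0625, and δ = 0.0626 × √61 = 0.49, which gives about 8%.

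**Step 4: attention.** Suppose 70% are coded 1 (assumed). Dichotomising a normal variable there multiplies its correlation by 0.348/√(0.7 × 0.3) = 0.76, so r is -0.76ab.

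| Assumed (a, -b) | ab | Use, as planned | Use, with Ethic_score | Attention, as planned |
|---|---|---|---|---|
| (0.3, -0.2) | 0.06 | 7-8% | 5% | 6-7% |
| (0.3, -0.3) | 0.09 | 11% | 5% | 8% |
| (0.5, -0.3) | 0.15 | 22% | 6% | 15% |
| (0.5, -0.5) | 0.25 | 52% | 8% | 33% |

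Simulation of 20,000 label arms per setting agrees to within about two points. With Ethic_score added, the simulated rates for attention are about 5-6%.

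**Step 5: dependence on scale.** If *b* is instead the correlation with the PEF of a single dish, and the two dishes are otherwise unrelated, the person-mean correlation is b/√[(1 + b²)/2], which turns 0.3 into 0.41 and 0.5 into 0.63. The as-planned rates for use at the last three settings become about 16%, 37% and 74%. The table above uses the more conservative scale.

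**The case against.** Several points on the other side stand.

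- **The size is assumed.** No document gives these correlations. Vegetarians and vegans are excluded, and the Background reports that only 15% of European respondents named the environment as an important driver of food choice. Both facts could point to weaker links, where the rate is close to nominal.
- **Objective 2.2 states moderation.** It says "The environmental label will be more effective in reducing the environmental impact of food choices in participants with higher levels of ethical concern". A reader might infer that the plan itself expects concerned people to choose low-PEF food without a label. It does not say so. The Ethic_score main effect in Model 2.2 has to be there to support the interaction, and is not a hypothesis of its own.
- **Adjustment can bias too.** Ethic_score is collected after all shopping and after the questions on label attention and use. If use and PEF were unrelated but each shaped the score, adjusting would create a false association. With influences of 0.3 and -0.3, the partial correlation is 0.09/0.91 = 0.099, and δ = 0.099 × 7.81 = 0.77 gives about 12% rejections. With 0.5 and -0.5 it is about 77%. The spurious sign is the opposite one: more use with higher PEF. This scenario needs a general motive scale to be driven wholly by one session. With mainly confounding and a small reverse influence, the adjusted test stays near 6%. The point does not defeat adjustment, but it does argue against replacing the planned model with the adjusted one.
- **The models are exploratory.** No hypothesis is attached to them, and the introductory sentence covers all of Table 6. That lowers the stakes but does not remove the confounding.

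**Conclusion.** The point holds as a possibility, with a size that depends on assumptions. Two self-selected predictors are studied within one arm with no participant covariate, so they can show an apparent effect of use when the label is inert. For use, the false-positive rate is about 7-8% at correlations (0.3, -0.2) and about 50% at (0.5, -0.5). There is no inflation if concern is unrelated to either use or PEF. For attention the rates are lower, and because the label is explained to the whole arm this variable may differ little between participants.

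A reader might infer that a significant coefficient is to be expected from an inert label. The figures do not support that: on the person-mean scale it reaches about an even chance only for use at the strongest setting, and is the less likely outcome in the others. Nor does the point touch the randomised label comparisons in Models 1.1, 1.2 and 2.1 or the label-by-concern test in Model 2.2. The importance is minor.

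**What to change.** In Table 6, report the attention model and the use model twice: as planned, and with Ethic_score added. State that the coefficients describe associations within the label arm and are not effects of the label. As a check, show next to them the slope of PEF on Ethic_score in the no-label arm, which Model 2.2 already yields when no label is the reference level. A slope near zero there would make this confounding less plausible, though the score is collected after shopping in that arm too.

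The cost is one extra covariate in two exploratory models with about 65 participants, and a sentence of text. No new data are needed. Because Ethic_score is measured with error and late in the session, the adjusted result may keep some confounding or carry some bias of its own. If the two versions disagree, the text should say that the data cannot separate label use from prior concern.
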